3.2 Baseline Values

For all safety assessments, baseline will be defined as the last non-missing value prior to SPN-812 dosing in the 812P311 study.

For all efficacy assessments, subjects enrolled into $812P311 \le 7$ days after their last 812P306 visit, the "baseline" efficacy assessment is defined as the assessment that subject completed at Visit 2 in 812P306 prior to the first dose of SPN-812 in 812P306. Additionally, for subjects enrolled into 812P311 > 7 days after their last 812P306 visit, the baseline efficacy assessment is defined as the assessment that was completed at Visit 1 in 812P311 prior to the first dose SPN-812 in 812P311.

All post-baseline assessments are defined as any assessments that were completed after the first dose of SPN-812 in the 812P311 study.

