# 3. INVESTIGATIONAL STUDY PLAN

# 3.1. Overall Study Design and Plan

This is an open-label, long-term, multicenter, flexible-dose study of SPN-812 in adults diagnosed with ADHD. Up to 366 subjects will be enrolled. Subjects who have completed Study 812P306 (a randomized, double-blind, placebo-controlled study of SPN-812 for the treatment of ADHD) will be eligible for enrollment into the Study 812P311. Interest and suitability will be ascertained at the last 1 to 2 visits of 812P306 to allow immediate enrollment into Study 812P311 for subjects who complete Study 812P306.

For subjects who complete Study 812P306 and rollover into Study 812P311 on the same day as or ≤7 days after 812P306 EOS visit, use INCLUSION/EXCLUSION CRITERIA 'A' (Section 3.3.2.) and follow SCHEDULE 'A' (Table 1; Figure 1). All efficacy and safety assessments collected at the subject's end of study (EOS) Visit (812P306) will serve as their efficacy and safety assessments for Visit 1 (812P311).

For subjects who complete Study 812P306, but who rollover into Study 812P311 more than 7 days after their EOS Visit (812P306), use **INCLUSION/EXCLUSION CRITERIA 'B'** (Section 3.3.3.) and follow **SCHEDULE 'B'** (Table 2; Figure 2). All efficacy and safety assessments will be collected at a screening visit (Visit 'S') to determine eligibility, and subjects will return to the clinical site for Visit 1 within 28 days of screening to make final eligibility determination and complete baseline efficacy and safety assessments.

*De novo* subjects (individuals who did not screen/enroll in Study 812P306) may screen and, if eligible, enroll in Study 812P311, but only after a "Note To File" has been submitted by the Sponsor to the IRB and approved. The clinical sites will be notified when the approval is granted. For these subjects, use INCLUSION/EXCLUSION CRITERIA 'B' (Section 3.3.3. ) and follow SCHEDULE 'B' (Table 2; Figure 2). Subjects who follow SCHEDULE 'B' and are taking any prohibited medications at screening (e.g., ADHD medications) should discontinue use (washout) at least 7-days prior to first dose of OLE SM.

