### 6.1.4. Clinical Global Impression – Improvement (CGI-I)

The CGI scale was developed to provide a brief, stand-alone assessment of the clinician's view of a subject's global functioning prior to and after administration of SM (Guy, 1976). The Clinical Global Impression – Improvement scale (CGI-I;

) is an assessment of how much the patient's illness has improved or worsened relative to a baseline state at the beginning of treatment. The Investigator/rater should consider their total clinical experience with the subject who has ADHD and rate improvement in the subject's condition compared to his/her's baseline assessment at the beginning of the subject's randomized, double-blind, placebo-controlled study. The CGI-S score obtained at the baseline serves as a good basis for making this assessment. The CGI-I is evaluated on a 7-point scale with 1 = Very much improved, 2 = Much improved, 3 = Minimally improved, 4 = No change, 5 = Minimally worse, 6 = Much worse, and 7 = Very much worse. Successful therapy is indicated by a lower overall score in subsequent testing.

Please note the following before assessing CGI-I:

- For subjects who follow **SCHEDULE** 'A', Baseline = Visit 2 (812P306)
- For subjects who follow **SCHEDULE** 'B', Baseline = Visit 1 (812P311)

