# 7.8. Efficacy Analysis

The efficacy analysis will be based on the safety population. Each efficacy endpoint will be listed and summarized descriptively by group of the optimized dose, if applicable. In addition, if applicable, subjects who received adjunctive stimulant therapy will be identified by flagging for categorical summary. Total and subscale scores/points for AISRS, CGI-S, CGI-I, GAD-7, BRIEF-A, SDQ, and AAQoL will be summarized by optimized dose (if applicable) and visit and will be examined. Baseline will be defined for all subjects as the last non-missing value prior to SPN-812 dosing in Study 812P311.

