3 STATISTICAL METHODS

3.1 General Methods

Premier Research, the designated CRO, will perform all statistical analysis using SAS version 9.4 or higher. Premier Research will be responsible for creating table, listing, and figure reports by SAS programming and delivering the reports, as well as the programs, to Supernus at study completion.

All analyses will be based on subjects who received any amount of study drug in Study 812P311. This will be referred to as the Safety Population. Since subjects received variable dosing in this study, all subject data will be summarized together under All SPN-812.

For categorical variables, summary statistics will include the number and percentage of subjects within each category (with a category for missing data). Percentages will be based on the total number of subjects with non-missing data. For continuous variables, summary statistics will include the number of non-missing observations, mean, standard deviation (SD), median, and interquartile range (Q1, Q3), minimum, maximum.

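### SAP 3.2 departs without explanation from the Protocol 7.8 efficacy baseline and pools changes measured from two studies' baselines, so change during the extension cannot be separated out

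*SAP*

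**What the plan says.** - **Protocol 7.8:** "Baseline will be defined for all subjects as the last non-missing value prior to SPN-812 dosing in Study 812P311". Schedule A covers 812P306 completers who enter within 7 days of their end-of-study (EOS) visit. Protocol 3.1 uses their 812P306 EOS assessments as 812P311 Visit 1, so under 7.8 the EOS value is their baseline.
- **SAP 3.2, efficacy:** for subjects enrolled within 7 days of their last 812P306 visit, baseline is "the assessment that subject completed at Visit 2 in 812P306 prior to the first dose of SPN-812 in 812P306". For those enrolled later, "the baseline efficacy assessment is defined as the assessment that was completed at Visit 1 in 812P311".
- **SAP 3.2, safety:** "For all safety assessments, baseline will be defined as the last non-missing value prior to SPN-812 dosing in the 812P311 study". This is the rule that the protocol gives for efficacy.
- **SAP 3.2, post-baseline:** "any assessments that were completed after the first dose of SPN-812 in the 812P311 study".
- **SAP 3.1:** "all subject data will be summarized together under All SPN-812". The titles of Tables 11.1 to 11.11 and of the efficacy figures show no split by entry route. SAP 3.3 uses observed data only.
- **Protocol 6.1.4:** the CGI-I rater compares with 812P306 Visit 2 for Schedule A and with 812P311 Visit 1 for Schedule B.
- **Protocol 7.1:** where statistical methods differ, the SAP overrides the protocol.

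**The concern.** The SAP changes the efficacy baseline for Schedule A without saying that it does so or why. It then averages two different quantities. For Schedule A, the change runs from before double-blind treatment, through 812P306, into the extension. For Schedule B, it starts at extension entry.

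The Schedule A figure therefore carries whatever happened in 812P306, including change on placebo. A reader of the pooled tables cannot tell what arose during the extension. The AISRS 30% and 50% responder rates inherit the same baseline. Because only observed data are used, the pooled mean can also move from visit to visit if the two routes drop out at different rates, even when no subject changes.

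For the same Schedule A subject, safety change and efficacy change also start at different times.

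**Working it through.** The plan states no figure to reproduce: there is no sample size calculation, no expected Schedule A share and no 812P306 result. The check compares the two definitions algebraically and then with assumed inputs.

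**1. Gap between the definitions.** Count reductions in AISRS as positive. Let p be the Schedule A share, g the mean reduction from 812P306 Visit 2 to EOS in Schedule A, a the further Schedule A reduction in the extension, and b the Schedule B reduction from 812P311 Visit 1. For Schedule B the two documents essentially agree.

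- SAP: p(g + a) + (1 − p)b
- Protocol: pa + (1 − p)b
- Difference: p × g, whatever a and b are

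**2. Size, with assumed p = 0.6 to 0.9 and g = 10 to 15 points.**

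- Smallest: 0.6 × 10 = 6.0
- Largest: 0.9 × 15 = 13.5

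**3. One worked case, assuming p = 0.8, a = 5, b = 12.**

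- SAP, g = 10: 0.8 × 15 + 0.2 × 12 = 14.4
- SAP, g = 15: 0.8 × 20 + 0.2 × 12 = 18.4
- Protocol: 0.8 × 5 + 0.2 × 12 = 6.4

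The differences, 8.0 and 12.0, equal p × g.

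**4. How much of the SAP figure comes from 812P306.** The share is pg / [p(g + a) + (1 − p)b]. With a = 5 and b = 12:

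- p = 0.6, g = 10: 6.0 / 13.8 = 43%
- p = 0.9, g = 15: 13.5 / 19.2 = 70%

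A wider grid used p = 0.25, 0.50, 0.75, 0.95; g = 5, 10, 15; a = 2, 5, 10; b = 10, 15, 20. Over its 108 combinations the share runs from 7% to 86%. It exceeds half in 30: none of 27 at p = 0.25, 1 at 0.50, 11 at 0.75 and 18 at 0.95.

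**5. Responder rates, with assumed scores of 38 at 812P306 Visit 2 and 26 at EOS.**

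| Extension score | Reduction, SAP baseline | Reduction, protocol baseline |
|---|---|---|
| 26 | (38 − 26)/38 = 31.6% | (26 − 26)/26 = 0% |
| 18 | (38 − 18)/38 = 52.6% | (26 − 18)/26 = 30.8% |

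The first subject does not change in the extension, yet counts as a 30% responder under the SAP. The second is a 50% responder under the SAP but only a 30% responder under the protocol.

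**6. Drift with schedule mix, a = 5 and b = 12, no change within any subject.** As p moves from 0.6 to 0.9:

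- SAP, g = 10: 13.8 to 14.7
- SAP, g = 15: 16.8 to 19.2
- Protocol: 7.8 to 5.7

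The drift arises under either rule; only a display by route removes it.

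**7. Which outputs are affected.** The baseline enters the change tables (11.1, 11.2, 11.6 to 11.10), their figures, and the AISRS responder table (11.11). The CGI-S responder rate (11.3) uses the current score alone. CGI-I (11.4, 11.5) is rated against the Protocol 6.1.4 anchors and cannot be re-anchored afterwards.

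**8. A gap in the rule.** SAP 3.2 is worded by time since the last 812P306 visit. De novo subjects, whom Protocol 3.1 may admit, have no such visit and so no explicit efficacy baseline.

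**The case against.** The case for the SAP is substantial.

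- **Which rule applies is settled.** Protocol 7.1 gives the SAP precedence. A reader might infer that the baseline is undecided; it is not. What stands is an unexplained departure.
- **The SAP's anchors have a source in the protocol.** They are those of Protocol 6.1.4. Applying 7.8 literally would put AISRS and CGI-I on different reference points for Schedule A.
- **Both SAP anchors approximate a pre-treatment state.** Schedule B requires AISRS of at least 24 and CGI-S of at least 4 at screening (Protocol 3.3.3.1), with a washout of prohibited drugs. Schedule A's 812P306 Visit 2 precedes double-blind dosing. The protocol rule would pool end-of-treatment values with Schedule B entry values. With a = 5 and b = 12, the routes differ by 7 points under the protocol rule and by 3 (g = 10) or 8 (g = 15) under the SAP rule. Reverting to 7.8 alone would not remove the mixture.
- **Efficacy is secondary, descriptive and uncontrolled.** Individual results are listed.

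All of this stands, and it is why the SAP baseline should be kept. It does not justify pooling the routes without a split, or leaving out change from extension entry. Protocol 6.1.4 is a rating instruction for one scale and does not address how change scores are pooled.

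A reader might also infer that some subjects will be reported as responders at Visit 1, before any extension dose. The documents do not support this. SAP 3.2 counts as post-baseline only assessments after the first 812P311 dose, and no 812P306 scores are given. What can be said is that some response counted later may already have been present at entry.

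**Conclusion.** The point holds as one of interpretation. SAP 3.2 departs from Protocol 7.8 without explanation, and the pooled change scores and AISRS responder rates mix change since before 812P306 with change since extension entry. The two definitions differ by p × g: 6.0 to 13.5 AISRS points if 60-90% of subjects are on Schedule A and gained 10-15 points in 812P306. Those inputs are assumptions; the documents give neither.

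A reader might conclude that the pooled change is mostly improvement from 812P306. That is not shown. The 812P306 share falls on both sides of one half over plausible inputs, and is 43% at the lower end of the range used here (p = 0.6, g = 10). The supportable statement is that the pooled figure includes 812P306 change, possibly as the larger part.

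The primary safety objective is unaffected, since the safety baseline is extension entry for everyone. The change should be made because it is cheap and lets the study show what happened during the extension. The SAP's list of outputs gives table titles only, and its shells were not available; if they already split by route, the display part of this point falls away.

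**What to change.** Keep the SAP baseline and make these changes:

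1. In the change-from-baseline tables and the AISRS responder table, show Schedule A, Schedule B and overall.
2. For Schedule A, add change from 812P311 Visit 1, which is the 812P306 EOS value.
3. State in SAP 3.2 which baseline applies to de novo subjects. Also reword the Schedule A rule to refer to the first dose of double-blind medication, since subjects given placebo in 812P306 had no SPN-812 dose there.
4. State in the SAP that the efficacy baseline departs from Protocol 7.8, and give the reason. Consistency with Protocol 6.1.4 would serve.

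A further split of Schedule A by 812P306 arm is optional. It would show how much of the carried-in change arose on placebo.

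No new data are needed: the SAP already draws on 812P306 Visit 2, and the EOS values already serve as Visit 1. The cost is longer tables and a smaller change attributed to the extension itself.

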3.3 Handling of Missing Data

There will be no imputation made for missing data points and hence, only observed data will be used for analyses.

3.4 Computing Environment

All descriptive statistical analyses will be performed using SAS (Version 9.4), unless otherwise noted.

4 ANALYSES

4.1 Subject Disposition

The number and percentage of subjects that were dosed, completed the study, or discontinued early will be displayed. Reasons for early discontinuation will be tabulated.

4.2 Demographic Characteristics

Descriptive statistics for demographic characteristics will be calculated for all continuous variables and frequencies and percentages will be presented for categorical variables.

4.3 Study Drug Exposure

Duration of exposure in days will be calculated from the first and last dates of the study drug administration. The duration of exposure will be calculated as date of last dose minus date of first dose + 1. Duration of exposure (days) will be summarized by categories, descriptive statistics, and by age group (18 to 44, 45 to 65, and overall). The categories for duration of exposure are: 0 to <13, 13 to <26, 26 to <39, 39 to < 52, 52 to < 65, 65 to < 78, 78 to < 91, 91 to <104, 104 to < 117, 117 to < 130, 130 to < 144, and 144 or more weeks. The actual average daily dose (0 to ≤ 200 , 200 to ≤ 300 , 300 to ≤ 400 , 400 to ≤ 500 , and > 500 mg/day) will be summarized by duration of exposure categories and by age group. Descriptive statistics for planned dose (n, mean, SD, median, min, max, and Q1, Q3) will be summarized by visit and by age group. The actual average daily dose is calculated as dispensed SPN-812 in mg minus returned SPN-812 in mg divided by days taken SPN-812 across all available visits.

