On a case-by-case basis, a subject who did not complete Study 812P306 (e.g., randomized, dosed SM and had at least one post-baseline AISRS assessment and then early terminated) may be allowed to screen and, if eligible, enroll in Study 812P311, but only after receiving approval from the Site Investigator, Medical Monitor, and the Sponsor. For these subjects, use **INCLUSION/EXCLUSION CRITERIA 'B'** (Section 3.3.3.) and follow **SCHEDULE 'B'** (Table 2; Figure 2).

All subjects will initiate SPN-812 dosing at 200 mg/day once daily (QD) during the first 2 weeks of the study. At Visit 2 and all subsequent study visits, per the Investigator's discretion and based on Investigator's assessment of the subject's clinical response and tolerability, the dose of SPN-812 can be titrated up or tapered down in increments of 50 mg/day, 100 mg/day, 150 mg/day, or 200 mg/day per week to a target dose within the ranges between 200 and 600 mg/day. Additionally, after the first 12 weeks of dosing (after Visit 4), at the discretion of the Investigator and based on the subject's clinical

response, the optimized dose of SPN-812 may be supplemented with an adjunctive FDA-approved stimulant treatment (see Section 4.3.).

Following the day that the subject takes first dose of SPN-812 (Day 1), the subject will have a study visit every 2 weeks for the first 4 weeks of the study (Visit 2 and Visit 3). After Visit 3, study visits (Visits 4-22) will occur 12, 20, 28, 36, 44, 52, 60, 68, 76, 84, 92, 100, 108, 116, 124, 132, 140, 148 and 156 weeks after first dose of SPN-812 (approximately every 8 weeks). A Point of Care (POC) urine drug screen (Test 1 and 2) will be completed at Visits 1, 6, 8, 10, 12, 14, 16, 18, and 20 (Table 3). In addition, the site should conduct a follow-up phone call (FPC) with each subject 4 weeks after Study Visits 3 thru Visit 21 to assess adverse events, changes in concomitant medications and obtain results of home pregnancy test (FOCP only). Subjects will also be contacted for final safety follow-up (FPC) approximately 1 week after the End of Study (EOS) visit.

The timing of Study Visits 2-22 and FPCs should occur per the Schedule of Events and Assessments (**SCHEDULE 'A'** [Table 1] or **SCHEDULE 'B'** [Table 2]) by day of study relative to the date of subject's first dose of SPN-812.

Note: The same assessments/procedures are performed at Study Visits 2-22 between **SCHEDULE 'A'** and **SCHEDULE 'B'**.

[figure not shown]

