### 3.4. Completion of Study and Discontinuation of Subjects

Subjects will be considered to have completed the study if they complete all visits up to and including Visit 22 (EOS).

If SPN-812 is not approved for Adults at the time of Visit 22, subjects may choose to continue in the study; repeating Visit 21 procedures every 8 weeks (including FPC in 4 weeks after each subsequent study visit) until SPN-812 becomes approved and commercially available for Adults.

Subjects who are enrolled and dosed with SM, but who withdraw or are withdrawn from participation in the study by the Investigator before he/she finishes the study (i.e., prior to Visit 22), should complete an early termination (ET) Visit. Procedures listed for the EOS visit should be completed at the ET Visit.

All reasons for screen failure will be recorded.

The Investigator(s) or subjects themselves may stop SM treatment at any time for safety or personal reasons. A subject is free to withdraw from the study at any time for any reason without prejudice to their future medical care by the physician or at the institution.

This document is confidential. It contains proprietary information of Supernus® Pharmaceuticals, Inc. Any viewing or disclosure of such information that is not authorized in writing by the Sponsor is strictly prohibited. Such information may be used solely for the purpose of reviewing or performing this study.

The Sponsor may also withdraw subject participation in the study without consent for any reason, but is in the best interest of subject safety. The withdrawal of a subject from the study should be discussed where possible with the Medical Monitor and Clinical Research Associate (CRA) before the subject stops SM. Subjects removed from the study for any reason will not be replaced.

Reasons for a subject's early discontinuation may include:

- Subject lost to follow-up
- Subject's withdrawal of consent
- Investigator ended subject's participation in study
- Other

The primary reason for the subject's early discontinuation must be recorded in the subject's medical record and on the electronic case report form (eCRF). If a subject is withdrawn for more than one reason, each reason should be documented in the source document and the most medically significant reason should be entered on the eCRF.

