### Doses:

- 200 mg/day = (200 mg capsule × 1) [once daily]
- 250 mg/day = (100 mg capsule × 1) + (150 mg capsule × 1) [once daily]
- 300 mg/day = (200 mg capsule × 1) + (100 mg capsule × 1) [once daily]
- 350 mg/day = (200 mg capsule × 1) + (150 mg capsule × 1) [once daily])
- 400 mg/day = (200 mg capsule × 2) [once daily]
- 450 mg/day = (150 mg capsule × 3) [once daily]
- 500 mg/day = (200 mg capsule × 2) + (100 mg capsule × 1) [once daily]
- 550 mg/day = (200 mg capsule × 2) + (150 mg capsule × 1) [once daily]
- 600 mg/day = (200 mg capsule × 3) [once daily]

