2.4 Study Drug Exposure

Study drug exposure is collected as both actual and planned dose and duration of exposure to SPN-812.

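### SAP 4.3 gives no rule for drug supplies that are never returned or counted, so the actual average daily dose in Table 3.3 depends on how the formula is read, and its category limits fall on prescribed dose levels

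*SAP*

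**What the plan says.** SAP 2.4 states: "Study drug exposure is collected as both actual and planned dose and duration of exposure to SPN-812". SAP 4.3 then derives the actual average daily dose as "dispensed SPN-812 in mg minus returned SPN-812 in mg divided by days taken SPN-812 across all available visits". The only day count it defines nearby is the duration: "The duration of exposure will be calculated as date of last dose minus date of first dose + 1". The averages are grouped as "0 to ≤ 200 , 200 to ≤ 300 , 300 to ≤ 400 , 400 to ≤ 500", with an open category above 500 mg/day, and reported by duration of exposure and age group in Table 3.3. SAP 3.3 rules out imputation and restricts analyses to observed data.

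Protocol 3.1 allows titration "to a target dose within the ranges between 200 and 600 mg/day". The dose list in Protocol 4.2 has nine levels in 50 mg steps, from "200 mg/day = (200 mg capsule × 1) [once daily]" to "600 mg/day = (200 mg capsule × 3) [once daily]". From Visit 3 on, scheduled visits are eight weeks apart.

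On returns, Protocol 3.4 asks subjects who leave early to attend an early termination visit with the end-of-study procedures. Protocol 5.1.5 lists drug return among those procedures, and Protocol 4.6 requires all used and unused supplies to come back by the end of the study. Protocol 3.4 also lists "Subject lost to follow-up" as a reason for discontinuation. Neither document says how the dose average treats a supply that does not come back.

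**The concern.** Under a dispensed-minus-returned rule, a capsule with no recorded return is a capsule taken. If a subject stops attending with most of an eight-week supply at home, the numerator holds the whole supply while the denominator stops at the last recorded dose. The average can then exceed the dose prescribed, and even the 600 mg/day maximum.

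The category limits add a second problem. Four of them are doses that subjects are actually prescribed, so a small counting error can change the category. The exposure is greatest at 200 mg: it is the lowest level, so there is no earlier lower-dose period to pull the average below the limit.

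The study's primary objective is long-term safety data. Table 3.3 is the only summary table of how much drug was actually taken and for how long. Two programmers who read SAP 4.3 differently could produce different versions of it.

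**Working it through.** The documents state no average dose to reproduce, so the check applies the SAP formula to example subjects.

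**Inputs from the documents.** Visit days 1, 15, 29, 85, then every 56 days to 1093; 200 mg/day for the first 14 days; dose levels 200 to 600 mg/day; category limits 200, 300, 400 and 500, upper limit included.

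**Assumptions.** The supply is 56 days, or 63 with a week's overage (not given in the documents). Every dose is taken up to the last dose date. The days in the denominator run from first to last dose.

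**1. Literal reading: last supply not returned, all of it counted as taken.** The subject takes 200 mg for 14 days, then 400 mg. The outstanding supply is 56 × 400 = 22,400 mg, or 63 × 400 = 25,200 mg.

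| Last dose | True mg taken | True average | Formula average |
|---|---|---|---|
| Day 85 | 14×200 + 71×400 = 31,200 | 31,200/85 = 367 | 53,600/85 = 631 to 56,400/85 = 664 |
| Day 113 | 14×200 + 99×400 = 42,400 | 42,400/113 = 375 | 53,600/113 = 474 to 56,400/113 = 499 |
| Day 365 | 14×200 + 351×400 = 143,200 | 143,200/365 = 392 | 165,600/365 = 454 to 168,400/365 = 461 |

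The true category is 300 to 400 in each row. The formula puts the first row above 500 and the other two in 400 to 500. In the first and third rows the subject has taken none of the outstanding supply. In the second row, four weeks of it have been taken.

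**2. Other readings, for the Day 113 subject (true 375).**
- Uncounted interval dropped from the numerator only: 31,200/113 = 276, one category too low.
- Dropped from numerator and denominator: 31,200/85 = 367, in the correct category.
- All unused drug returned at early termination: 42,400/113 = 375, no error.

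The same holds at 200 mg with last dose on Day 36 and supplies running to Day 84. The literal formula gives 84×200/36 = 467, numerator-only gives 28×200/36 = 156, and the true value is 200.

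**3. Category limits.** A 200 mg subject who completes with one capsule lost has (1093×200 + 200)/1093 = 200.18 mg/day and leaves the lowest category. Higher targets have slack from the lower starting dose. Slack is the titration shortfall divided by the target dose, with at most 400 mg/day in days 15 to 21:
- 300 mg: 1,400/300 = 4.7 days
- 400 mg: 2,800/400 = 7.0 days
- 500 mg: (14×300 + 7×100)/500 = 9.8 days
- 600 mg: (14×400 + 7×200)/600 = 11.7 days; here this is the slack before the average passes 600, since no category limit lies above 500

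**4. How often the category moves up if nothing from the last supply is returned.** This takes each last-dose day from 1 to 1092 once, with supply exactly to the next scheduled visit. The figures are shares of possible days, not predicted shares of subjects.

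| Target (mg/day) | 200 | 250 | 300 | 350 | 400 | 450 | 500 | 550 | 600 |
|---|---|---|---|---|---|---|---|---|---|
| Category moves up | 98% | 11% | 91% | 15% | 86% | 18% | 82% | 10% | 6% |

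The average exceeds 600 mg/day on 77% of days at a 600 mg target, 17% at 550, 7.5% at 500, and 3% or less at 400 and below.

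**The case against.** The strongest reply is that the error needs a supply that is neither returned nor counted, and the protocol is written to prevent that. Subjects who leave early are to attend a termination visit, drug return is one of its procedures, and all supplies and empty containers must come back by study end. With full return the formula is exact. This stands as far as it goes, but it does not cover a subject who is lost to follow-up, and the protocol itself expects some.

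A second reply is that restricting analyses to observed data, together with averaging over available visits, already means that an uncounted interval is left out. Treating a missing return as zero would be a form of imputation. That is a fair reading, but the SAP does not state it, and it does not say whether the matching days leave the denominator. That choice decides whether the error vanishes or turns downward.

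A reader might infer that dropouts as a group are pushed into higher dose categories, or that the error always runs upward. The documents do not support either: the non-return rate is unknown and the direction depends on the reading. A reader might also infer that adverse event or efficacy results by dose are distorted. They are not, because SAP 3.1 pools all subjects under All SPN-812, and planned dose is summarized separately in Table 3.2. Averages above 600 mg/day would sit unseen in the open top category, although Listing 3 would still show the dosing records.

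Finally, the examples use 400 mg, which lies on a limit. Subjects on 250, 350, 450, 550 or 600 mg seldom change category.

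**Conclusion.** SAP 4.3 is incomplete on uncounted supplies and on the denominator, and Table 3.3 can change materially with the reading chosen. For the 400 mg example with last dose on Day 113, the same subject scores 474 to 499, 367 or 276 mg/day against a true 375. Under the literal reading the distortion is largest in the short-duration rows, where one outstanding supply is large relative to the days on drug. These sizes rest on an assumed 56 to 63 day supply and on none of it being returned. How many subjects would be affected cannot be estimated from the documents.

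The placement of the limits is a separate, smaller flaw. It is sharp at 200 mg, where one capsule is enough, and it affects completers as well as dropouts. At 300, 400 and 500 mg it takes roughly 5 to 10 days of unreturned drug. The consequence is limited to the description of exposure by actual dose. No safety or efficacy result depends on it, but in a long-term safety study the table is worth getting right.

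**What to change.** In SAP 4.3:

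1. Include in the average only dispensing intervals whose supply was returned and counted, and use the days of those same intervals as the denominator.
2. Define the days in the denominator explicitly.
3. Report the number of intervals excluded for lack of a count.
4. Place the category limits between dose levels, for example <225, 225 to <325, 325 to <425, 425 to <525 and ≥525 mg/day.

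Item 4 does not replace item 1. With nothing returned, a 200 mg subject with last dose on Day 372 and supplies to Day 420 averages 420×200/372 = 226 and would still cross 225.

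A time-weighted mean of the recorded dose may be added as a supporting summary. It should not replace the count-based figure: it assumes intake as instructed and largely repeats the planned-dose summary in Table 3.2.

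The cost is a few lines of SAP text and reprogramming of one derived variable. The drawback is that uncounted intervals drop out of the average, so a subject with no counted interval has no value. The reported number of exclusions makes that loss visible.
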